8.Experimental design: : A two-arm parallel trial design was carried out.The participants who underwent PCNL with one-handed lithotripsy were selected as the experimental group, and the participants who underwent traditional PCNL were selected as the control group.Prospective exploration studies were conducted on a 1:1 basis.

9.Site: This was a single-center study conducted at the First Affiliated Hospital of the University of South China

10.. Inclusion and exclusion criteria:1.Participants who met the the applications of PCNL surgery in the 2019 Chinese Guidelines for the Diagnosis and Treatment of Urological Diseases; 2. Participants who agree to undergo PCNL with one-handed lithotripsy.Exclusion Criteria: 1).Obvious surgical contraindications, such as severe heart and lung insufficiency, abnormal coagulatory function.2) If the following variations occurred during the operation: a finding that pyonephrosis demanded the treatment of nephrostomy,channel bleeding that was required to maintain a nephrostomy tube,or incomplete postoperative clinical data will be recorded by the study recruitment flow chart, but not included in the final data analysis

11.Intervention measures:

a. According to the randomization, the same associate chief urologist performed PCNL with one-handed lithotripsy or traditional PCNL;

b.During the perioperative period, participants were given comprehensive blood biochemical examination and imaging evaluation, and antibiotics (second-generation cephalosporins or penicillins) were prophylactic.Participants with hypertension, diabetes and other comorbidities were given relevant drugs to control the tolerable level of surgery.

c. Implementation process of PCNL with one-handed lithotripsy:

a).After general anesthesia, the patient was placed in lithotomy position, routinely

[figure not shown]

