disinfected and covered with towels. Transurethral cystoscopy/ureteroscopy was performed to observe the ureteral opening on the affected side, and the ureteral catheter was retrograde inserted at a depth of 15 to 25cm. Exit the ureteroscope and fix the ureteral catheter on the urinary catheter. Then, the patient was moved to prone position, disinfected again and covered with towel, suffer renal biopsy under ultrasound guided look straight into the target under the calyces, syringe after water injection and suction is smooth, the guide wire guided by micro fascia dilator (Fr16 or Fr18) continuous build percutaneous renal channel expansion. Holmium laser was used for lithotripsy

b). According to different lithotripsy methods, the operation was randomly divided into group 1 (one-handed lithotripsy group): using one hand to control the nephroscope and laser fiber at the same time, the other hand to adjust the depth and angle of the sheath at same time. Group 2 (traditional lithotripsy group) : lithotripsy was carried out by holding the nephroscope with one hand and controlling the laser fiber with the other one. It was often necessary to stop the lithotripsy to adjust the depth and angle of the sheath.

c). After the broken stones were removed, the ureteropelvic opening was located, the guide wire was placed anteriorly, and the ureteral stent was placed under the guidance of the guide wire. After no residual calculi were detected under the nephroscope, the endoscope was removed and the nephrostomy tube was indwelled and fixed. The incision skin is then sutured.

12. Outcome measures : The primary clinical end point are operative time 、 stone clearance rate 、 number of tracts 、 rate of second operation 、 rate of auxiliary procedure 、 intraoperative renal pelvis mucosal injury rate 、 the incidence of postoperative complications (including postoperative fever, bleeding, pain, and changes in renal function; Ureterostone street was formed after operation. Air-fluid chest after operation) ; The secondary clinical end points were operation time, hospital stay, hospital cost.

13. Recruitment flow chart:

14. Sample size: Combined with the number of outpatient calculi patients and the number of PCNL surgeries in our department of Urology each year, we planned to initially include 100 patients with renal and/or upper ureteral calculi who underwent traditional PCNL surgery in our hospital from November 2022 to November 2023, and randomly assigned at 1:1.

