15. Participants: Patients with upper urinary stones attending the Urology Clinic of the First Affiliated Hospital of the University of South China were recruited

16. Allocation sequence generation, allocation hiding, implementation methods: Using the coin toss method, patients with the flip side of the coin were divided into PCNL surgery group using one-handed lithotripsy technique (group 1), and patients with the reverse side of the coin were assigned to the traditional PCNL procedure group (group 2). This process takes place in the operating room

17. Blinding: : In a single-blind approach, patients are told to participate in a clinical trial but are not informed about the specific intervention, while the person administering the intervention is clearly informed.

18. Data collection: The measured data of all the required: : 1. The demographic data, stone characteristics and preoperative baseline data, including the proportion of gender, age, body mass index (BMI) and basic diseases distribution, location, stones, stone maximum cross-sectional area, the longest diameter antler shape proportion and

pelvic effusion width, partial side and puncture operation, etc.2.Data of the main end points included:operative time、 stone clearance rate、 number of tracts、 rate of second operation、 rate of auxiliary procedure、 intraoperative renal pelvis mucosal injury rate、 the incidence of postoperative complications (including postoperative fever, bleeding, pain, and changes in renal function; Ureterostone street was formed after operation. Air-fluid chest after operation) ; Secondary end points included:postoperative renal function changes, operative blood loss, postoperative bleeding rate, postoperative patient pain score, postoperative inflammation changes。

19. Statistical analysis plan: SPSS26.0 statistical software was used for analysis.

Measurement data were expressed as mean \pm standard deviation ($X \pm S$) and t-test was used. Enumeration data were expressed as frequency and percentage by X^2 or Fisher exact test. Rank sum test was used for rank data. $P < 0.05$ was considered statistically significant.

20.Ethical approval: This trial was a human life science and medical study and was approved by the Medical Ethics Committee of the First Affiliated Hospital of the University of South China. (No: 2022111120001)

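### Section 16 announces allocation concealment but prescribes only an operating-room coin toss that leaves no trace, so the allocation cannot be verified

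*Protocol*

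**What the plan says.** Section 16 of the protocol is headed "Allocation sequence generation, allocation hiding, implementation methods". The text below it has two elements. The first is the method: "Using the coin toss method, patients with the flip side of the coin were divided into PCNL surgery group" using the one-handed technique, with the reverse face giving the traditional procedure. The second is the place: "This process takes place in the operating room".

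Other sections bear on this:

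- Section 5 lists the duties of the study leader and the postgraduate. Allocation is not among them.
- Section 11a has one operator for both arms and ties treatment to the allocation: "According to the randomization, the same associate chief urologist performed PCNL with one-handed lithotripsy or traditional PCNL".
- Section 11c(b), placed after the access steps, says: "According to different lithotripsy methods, the operation was randomly divided into group 1 (one-handed lithotripsy group").
- Section 17 blinds the patient, "while the person administering the intervention is clearly informed".
- Section 10 lists events that remove a patient from the analysis, beginning "If the following variations occurred during the operation: a finding that pyonephrosis demanded the treatment of nephrostomy". It adds channel bleeding and incomplete postoperative data. Such cases "will be recorded by the study recruitment flow chart, but not included in the final data analysis".
- Section 14 plans 100 patients, allocated 1:1.

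**The concern.** Section 16 sets out to fix how the sequence is generated, hidden and carried out, so these are matters for this protocol and cannot be assumed to sit in an analysis plan. What it fixes is a method without independent evidence. The visible text does not say who tosses, that the first toss stands, that the result is written down, or when the toss happens relative to consent, eligibility checks, anaesthesia or access.

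The operator is unblinded, treats both arms, and can know the stone burden from the imaging described in section 11b. Endpoints such as operative time, stone clearance and number of tracts plausibly depend on stone complexity. If an unwelcome toss were repeated or set aside, the arms would differ at baseline for reasons other than chance, and nothing in the prescribed procedure would show it. Blinding the patient gives no protection here.

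The open moment also touches section 10. If pyonephrosis or channel bleeding is found during the operation, a recorded allocation time is needed to say whether the exclusion came before or after assignment.

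**Working it through.** **Reading the text.** For each element that would make the allocation checkable:

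| Element | Visible text |
|---|---|
| Method | Coin toss (section 16) |
| Place | Operating room (section 16) |
| Person who tosses | Not stated; not among the duties in section 5 |
| Rule against repeating a toss | Not stated |
| Record or witness | Not stated |
| Moment | Not stated; 11a suggests before surgery, 11c(b) mentions the division after access |
| Link from allocation to treatment | Stated (section 11a) |

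The protocol gives no figure on this point that could be reproduced. N = 100 is set from patient volume.

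**Could arm sizes alone reveal misuse?** For 100 fair tosses, the exact binomial gives P(exactly 50:50) = 0.080, P(larger arm ≥ 60) = 0.057 and P(larger arm ≥ 61) = 0.035. A two-sided exact test at 0.05 therefore flags only 61:39 or worse. Imbalance in numbers is itself minor: efficiency relative to 50:50 is 4 × 0.6 × 0.4 = 0.96 at 60:40.

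**Could arm sizes plus a staghorn comparison reveal it?** Everything beyond N = 100 and 1:1 is assumed:

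- S = 20, 30 or 40 patients have staghorn stones.
- A fraction r of the staghorn patients first tossed to group 1 is re-tossed once.
- All other tosses are honest.

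A re-toss changes the arm half the time, so the probability that a staghorn patient ends in group 1 is p1 = 0.5 − 0.25r. Expected re-tosses are 0.5 × S × r, and the net number moved is 0.25 × S × r.

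With r = 0.5, p1 = 0.375:

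- S = 20: 5 re-tosses, net 2.5 moved; shares 7.5/47.5 = 15.8% v 12.5/52.5 = 23.8%.
- S = 30: 7.5 re-tosses, net 3.75 moved; shares 11.25/46.25 = 24.3% v 18.75/53.75 = 34.9%.
- S = 40: 10 re-tosses, net 5 moved; shares 15/45 = 33.3% v 25/55 = 45.5%.

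Staghorn patients in group 1 are Binomial(S, p1) and other patients in group 1 are Binomial(100 − S, 0.5). I enumerated every outcome exactly. The baseline flag is a chi-square test without continuity correction at P < 0.05. The arm-total flag is group 1 ≤ 39 or ≥ 61.

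| Scenario | S | Baseline flag | Arm-total flag | Either |
|---|---|---|---|---|
| Honest, r = 0 | 20 | 0.051 | 0.035 | 0.084 |
| | 30 | 0.052 | 0.035 | 0.085 |
| | 40 | 0.055 | 0.035 | 0.088 |
| Half re-tossed, r = 0.5 | 20 | 0.168 | 0.058 | 0.219 |
| | 30 | 0.213 | 0.088 | 0.283 |
| | 40 | 0.243 | 0.133 | 0.348 |
| All re-tossed, r = 1 | 20 | 0.535 | 0.130 | 0.609 |
| | 30 | 0.666 | 0.267 | 0.763 |
| | 40 | 0.728 | 0.460 | 0.868 |

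Disregarding a fraction d of such tosses outright gives p1 = 0.5(1 − d). Thus d = 0.25 matches r = 0.5, and d = 0.5 matches r = 1.

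On these two checks, the moderate pattern passes unflagged in 65% to 78% of trials (1 − 0.348 to 1 − 0.219). The gross pattern is flagged in 61% to 87%.

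**The case against.** The best defence is that a fair coin tossed when needed is valid randomisation. There is no future sequence to discover, so it is concealed by nature until it lands. That stands: predictability is not the weakness. Section 11a also says treatment follows the randomisation, so the text does bind treatment to the toss. What is missing is a bar on tossing again and a record.

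The timing conflict is weak, which also stands. Section 11c(b) comes after steps common to both arms and may only mark where the techniques part. The place is fixed; the moment is not.

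On section 10, a reader might infer that no exclusion can be placed before or after allocation, or assigned to an arm. The documents do not support that. Exclusions for incomplete postoperative data always follow allocation, and if the toss precedes surgery so do the intraoperative ones. Only pyonephrosis or channel bleeding found before a late toss would be ambiguous. The section 13 flow chart, where these cases are to be recorded, is not shown, so whether it splits them by arm is unknown.

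The illustration is limited too. It uses one binary stone variable and the arm totals. Section 18 also collects cross-sectional area, longest diameter, location and pelvic effusion width, and detection from these was not evaluated.

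Finally, a logged toss by a non-operator would close the listed gaps, and a pre-made list can leak where a coin cannot. Both points are fair. The list has one advantage: it can be checked against the log afterwards, whereas a coin log shows only what someone wrote down.

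**Conclusion.** The concern holds as a lack of verifiability and should be fixed. Section 16 promises concealment and prescribes a method that leaves no independent trace, in a trial where one informed operator treats both arms.

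The 22% to 35% flagging rate (8% to 9% with honest tosses) rests on assumed staghorn numbers and on an assumed direction and rate of misuse. It covers staghorn share and arm totals only. It shows that those two checks are a poor substitute for a record when misuse is moderate; gross misuse would often be seen.

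A reader might go further and infer that allocation was manipulated, that the randomisation is invalid or the results biased. Nothing in the protocol suggests misuse, an honest toss would be sound, and no bias in any endpoint has been estimated.

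**What to change.** In section 16, replace the toss as follows:

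- An existing staff member who does not operate prepares a computer-generated simple (unblocked) 1:1 list of 100, held in sequentially numbered opaque sealed envelopes.
- Non-operating theatre staff open the next envelope at one stated moment, after consent and preoperative eligibility are confirmed.
- They log patient, envelope number and time before the operator is told.

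Word sections 11a and 11c(b) to agree with that moment. Report every section 10 exclusion after it by assigned arm, with the reason.

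The cost is a list, 100 envelopes and one log line per patient. The sample size does not change. Leaving the list unblocked keeps the coin's unpredictability and, like the coin, does not force equal arms. The downside is that the list must be kept sealed from the operator, a leak risk the coin does not have.

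That existing non-operating staff can do this is an assumption, since the protocol does not describe theatre staffing. If they cannot prepare and hold a list, the minimum repair is one binding toss, made and logged by a named non-operator at the stated moment before the operator is told.

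### Arms are formed by coin toss and Section 19 states only unadjusted tests, so chance imbalance in stone burden goes uncorrected; adjusting for preoperative staghorn status would recover precision at no cost

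*Protocol*

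**What the plan says.** Section 16 gives the method of allocation: "Using the coin toss method, patients with the flip side of the coin were divided into PCNL surgery group using one-handed lithotripsy technique"; the other face leads to traditional PCNL. It adds that "This process takes place in the operating room". It names no block, stratum or minimisation factor.

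The ratio appears twice. Section 8 says "Prospective exploration studies were conducted on a 1:1 basis", and Section 14 says "randomly assigned at 1:1". The planned number is also in Section 14 ("we planned to initially include 100 patients with renal and/or upper ureteral calculi"), and its basis is clinic and surgical volume ("Combined with the number of outpatient calculi patients and the number of PCNL surgeries in our department of Urology each year").

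Section 18 lists, with the demographic and preoperative baseline data, "stone maximum cross-sectional area, the longest diameter antler shape proportion". Staghorn shape and stone size are therefore recorded as baseline features.

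Section 19 assigns the t-test to measurement data, chi-square or Fisher's exact test to counts, and the rank sum test to ranked data. It mentions no covariate or stratum. Section 17 says that patients are not told the specific intervention, while "the person administering the intervention is clearly informed".

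**The concern.** Independent tosses balance the arms only on average. With about 100 patients, a noticeable difference in the share of staghorn stones is an ordinary event. Section 6 names staghorn and large stones among the reasons for PCNL, so stone burden will vary within the trial. It plausibly affects operative time, clearance, number of tracts and second operations, which Section 12 lists as primary endpoints.

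An unadjusted comparison carries any such imbalance into the observed difference and leaves the variation due to stone burden in the error term. What is at stake is precision, and how easily the single observed result can be read. Because the sample size rests on volume and no power is stated, there is no declared margin of precision to spare.

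**Working it through.** **Inputs.** From the protocol: n = 100, a fair coin, unadjusted tests. Assumed, because the protocol gives no figures: staghorn share p of 20% to 40%; staghorn operations 30 minutes longer; residual SD σ of operative time 20, 30 or 40 minutes. The planned number of 100 cannot be reproduced, since no effect size, SD, rate or power is given.

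**1. Arm sizes.** The number in one arm is Binomial(100, 0.5).
- P(exactly 50:50) = 8.0%
- P(55:45 or more uneven) = 36.8%
- P(60:40 or more uneven) = 5.7%

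Relative efficiency is 4·n₁·n₂/n². At 60:40 this is 4 × 60 × 40 / 100² = 0.96. For a difference of 0.56 SD, which 50:50 detects with 80% power at two-sided 0.05, power is 78.4% at 60:40 and 79.6% on average over the coin. Uneven arm sizes are not the problem.

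**2. Imbalance in staghorn share.** The SD of the between-arm difference is about √(4p(1−p)/n).
- p = 0.2: √(4 × 0.16 / 100) = 8.0 points
- p = 0.3: √(4 × 0.21 / 100) = 9.2 points
- p = 0.4: √(4 × 0.24 / 100) = 9.8 points

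Simulation of the coin (100,000 trials per share) gives a difference of 10 points or more in 22%, 28% and 31% of trials, and of 15 points or more in 6%, 10% and 13%.

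**3. Effect on operative time.** A 10-point imbalance moves the raw difference by 0.10 × 30 = 3 minutes. Against the unadjusted standard errors below, that is 3/8.6 = 0.35 to 3/4.8 = 0.63 of one standard error.

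**4. Precision with and without adjustment (p = 0.3).** Between-stratum variance is 0.3 × 0.7 × 30² = 189. In closed form, the unadjusted standard error is √(4(σ² + 189)/n) and the adjusted one is √(4σ²/n), ignoring small losses from uneven arms.

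| σ (min) | Unadjusted, closed form | Adjusted, closed form | Coin, unadjusted (simulated) | Coin, adjusted (simulated) | Stratified blocks, adjusted (simulated) |
|---|---|---|---|---|---|
| 20 | √(4 × 589/100) = 4.85 | 4.00 | 4.8 | 4.0 | 4.0 |
| 30 | √(4 × 1089/100) = 6.60 | 6.00 | 6.7 | 6.1 | 6.0 |
| 40 | √(4 × 1789/100) = 8.46 | 8.00 | 8.6 | 8.2 | 8.0 |

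In closed form, adjustment removes 189/589 = 32%, 189/1089 = 17% or 189/1789 = 11% of the variance. Nearly all the gain comes with the coin kept.

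**5. What blocks would add and cost.** With two strata and random blocks of 4 and 6, no simulated trial had a 10-point staghorn difference (5,000 runs per share). The price is predictability. Suppose an observer always guesses the arm that is behind in the stratum, and guesses at random when the arms are level. The expected number right is b/2 + 2^b/(2·C(b, b/2)) − 1/2 per block of size b.
- b = 4: 2 + 16/12 − 0.5 = 2.83
- b = 6: 3 + 64/40 − 0.5 = 4.10

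With both sizes equally likely, the proportion right is (2.83 + 4.10)/10 = 69%, against 50% for a coin. The observer does not need to know the block size, because every block ends level.

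**The case against.** The strongest reply is that nothing here is an error. A fair coin is a valid 1:1 scheme, and the unadjusted tests already allow for chance imbalance in their standard errors. In simulation under the assumptions above, the unadjusted t-test with coin allocation kept its type I error at 4.4% to 4.9%. This stands, and it rules out three stronger readings.

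- A reader might infer that the coin contradicts the 1:1 statements in Sections 8 and 14. It does not: those sections state a ratio and never promise 50 patients per arm.
- A reader might infer that a chance imbalance would make the result uninterpretable. The shift computed for a 10-point imbalance is well below one standard error.
- A reader might infer that the toss itself must go. Blocks add almost nothing once the analysis adjusts, and with one operator who knows the allocation and assignment made in the operating room, unpredictability is a real strength of the coin. Runs of one arm do not change this: the longest run in 100 tosses has a median of 7, and no harm from it has been shown.

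It can also be said that covariates belong in a separate analysis plan, which is not at hand. That would answer a complaint about silence. Here, however, Section 19 is itself headed as the statistical analysis plan and names the tests, all unadjusted, so the point concerns a stated method.

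**Conclusion.** The point holds as a matter of precision. With coin allocation and the unadjusted tests of Section 19, a difference of 10 points or more in staghorn share goes uncorrected in about 22% to 31% of trials, if 20% to 40% of patients have staghorn stones. Adjustment would cut the standard error for operative time from 4.8–8.6 to 4.0–8.2 minutes under the assumed 30% share, 30-minute effect and residual SD of 20 to 40 minutes. A weaker link between staghorn status and the outcome would give a smaller gain. No gain has been computed for the binary endpoints.

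This is neither a bias nor an internal contradiction. It is an improvement on the stated analysis using data the trial already plans to collect.

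**What to change.** In Section 19, pre-specify before any comparison of outcomes that the primary comparisons adjust for one named baseline stone feature: preoperative staghorn status (yes/no) or the recorded stone area. Use a linear model with arm and that term for continuous endpoints. For binary endpoints use a Mantel-Haenszel analysis across staghorn strata, or an equivalent. The unadjusted tests can remain as supporting analyses. The cost is a short amendment, with no extra patients, measurements or staff.

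Optionally, replace the toss in Section 16 with a computer-generated list, stratified by staghorn status, in randomly varying blocks. Do this only if the list is concealed and held by someone outside the operating team, which needs that person's time. It would balance the chosen feature closely. If stone area cut at its median were the stratum, it would remove only about 64% of the imbalance variance in area. The exclusions after allocation in Section 10 could disturb either balance, so adjustment would still be needed.

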Application of one-handed lithotripsy in percutaneous nephrolithotomy

Clinical study protocol

1. Title: Application of one-handed lithotripsy in percutaneous nephrolithotomy.
2. Trail registration: Clinical Trials Registry (<https://www.clinicaltrials.gov>) 。
3. Version number and date: Version number: V1.0 Version Date: November 19, 2022。
4. Funding: New technology of the First Affiliated Hospital of the University of South China
5. Investigator and responsibilities: [name], deputy chief physician (study leader) : trial design, surgical implementation, protocol management, and process guidance; Research group postgraduate: data collection and analysis, article writing and publication.
6. Research background and principle: Percutaneous nephrolithotomy(PCNL)is the treatment of choice for staghorn stone,complex renal caculi,large volume calcilo (especially ≥ 2 cm in diameter) .This procedure is the highest level of urology surgery and is characterized by high difficulty and high risk.Traditional PCNL usually adopt the left hand holding nephroscope to adjust depth and direction of the lens and the right hand to control the fiber for lithotripsy.It requires the operator to undergo long-term practical training to achieve tacit cooperation between the hands.There are analysis of the learning curve for percutaneous nephrolithotomy suggests that operators take at least 20 cases of PCNL to learn basic surgical skills, and at least 60 cases to initially master surgical competence.So, we propose a new surgical method - one-handed lithotripsy technique.The core of this technology is to use the same hand to hold the nephroscope and control the laser fiber,thereby avoiding the running-in problem of the two hands controlling the nephroscope and the laser fiber respectively, and the operator can continuously adjust the fiber and nephroscope to continuously crush the litholysis during the surgery, which significantly shortens the learning curve, operation time and difficulty of PCNL.Therefore, we believe that the promotion and

popularization of percutaneous nephroscopic with one-handed lithotripsy is of great clinical practical significance.

7.Objective: : The purpose of this study is to explore the safety and clinical efficacy of this new surgical method in the treatment of upper urinary calculi by combining the application of one-handed lithotripsy in the PCNL.

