21.Informed consent: All participants enrolled in the study signed a surgical consent and a clinical trial informed consent to collect and use the medical behavior information and biological samples for the study

22.Confidentiality measures: The identifiable information of the subjects is replaced by irrelevant character sequences to ensure that the relevant personal information of the subjects will not be disclosed in any form.

23.Declaration of Interest: There is no conflict of interest between the investigator and the organization.

24.. Data Acquisition: : When proper editing or review requirements are met, the study data may be obtained from the study manager after the study is completed.

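### Only the patient is masked: the protocol plans no masked recording of postoperative outcomes and no masked analysis, although it names a separate team member who could provide both

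*Protocol*

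**What the plan says.** Section 17 (Blinding) covers two parties. For the patient: "In a single-blind approach, patients are told to participate in a clinical trial but are not informed about the specific intervention". For the operator: "while the person administering the intervention is clearly informed". It is silent on the outcome assessor, the data collector and the analyst.

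Section 5 divides the work. The study leader has "trial design, surgical implementation, protocol management, and process guidance". The other role is listed as "Research group postgraduate: data collection and analysis, article writing and publication". Section 11 adds that "the same associate chief urologist performed PCNL with one-handed lithotripsy or traditional PCNL", so one operator, who cannot be masked, treats both arms.

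Section 12 lists the primary endpoints. They include stone clearance, second operation, auxiliary procedures, "intraoperative renal pelvis mucosal injury rate" and postoperative complications (fever, bleeding, pain, renal function change, steinstrasse, air or fluid in the chest). Neither Section 12 nor Section 18 says who judges them or by what method. Section 16 places the coin toss in the operating room.

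Section 22 provides that "The identifiable information of the subjects is replaced by irrelevant character sequences". This is a confidentiality measure.

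**The concern.** Randomisation makes the groups comparable at the start. It does not protect the outcomes from being recorded differently once the arm is known. Section 6 shows that the team proposes the technique and already regards it as better, so an expectation exists. The protocol defines none of the judgement-based endpoints, which leaves room for that expectation to act.

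The operator cannot be masked, but someone else collects the data. For outcomes that are determined after the operation, that person could work without knowing the arm. The protocol does not ask for this. If recording differs by arm, the comparison is biased, and a larger sample would not remove the bias.

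Who is masked during data collection is a design decision that Section 17 itself undertakes to make. A statistical analysis plan cannot later mask outcomes that have already been recorded.

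**Working it through.** **Step 1: who could know the arm.**

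| Role | Source | Arm known? |
|---|---|---|
| Patient | Section 17 | Meant to be masked |
| Operator | Sections 11 and 17 | Yes, unavoidably |
| Postgraduate (collection and analysis) | Section 5 | Not stated; nothing prevents it |

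**Step 2: which outcomes masked recording could protect.**

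| Outcome | Could the postgraduate record it masked? |
|---|---|
| Fever, bleeding, renal function, steinstrasse, chest complications | Yes |
| Stone clearance | Yes, if read from postoperative imaging. Not if it rests on the nephroscopic check in Section 11, which is the only residual-stone check described |
| Pain score | Supplied by the patient, who is the masked party; little to gain |
| Operative time, number of tracts, mucosal injury | No; they arise in theatre |
| Second operation, auxiliary procedure | Probably not; the decision may rest with the unmasked surgeon |

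**Step 3: possible size.** The protocol gives no expected rates, so there is no figure of its own to reproduce.

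Inputs from the protocol: 100 patients at 1:1, hence 50 per arm (Section 14); chi-square test at P < 0.05 (Section 19), taken as two-sided.

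Assumed inputs: a true clearance rate p that is the same in both arms, and a share f of one arm's failures recorded as successes.

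- Recorded rate in that arm: q = p + f(1 − p).
- Patients recoded on average: 50 × f(1 − p).
- Rejection rate: the sum of Bin(x; 50, q) × Bin(y; 50, p) over all pairs (x, y) with |x − y|/50 ÷ √[P(1 − P) × 2/50] > 1.96, where P = (x + y)/100. This is exact enumeration of the Pearson chi-square test.

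For p = 80% there are on average 50 × 0.20 = 10 failures per arm:

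| f | q | Patients recoded | False-positive rate |
|---|---|---|---|
| 0 | 80% | 0 | 5.2% |
| 10% | 82% | 1.0 | 6.0% |
| 25% | 85% | 2.5 | 10.6% |
| 40% | 88% | 4.0 | 20.3% |
| 50% | 90% | 5.0 | 30.3% |

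The result depends on the assumed clearance rate:

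| p | f = 0 | f = 25% | f = 50% |
|---|---|---|---|
| 70% | 5.0% | 13.7% | 44.3% |
| 80% | 5.2% | 10.6% | 30.3% |
| 90% | 5.1% | 6.9% | 14.5% |

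With equal recording in both arms, which masked recording aims to secure, the rate stays at about 5%.

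**The case against.** The strongest reply has five parts.

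1. *The text does not show unmasked recording.* A reader might infer that outcomes are recorded with knowledge of the arm. The protocol does not say so; it is silent on what the postgraduate knows. This objection stands, and the point is limited to the absence of any safeguard.

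2. *Masking reaches only some of the outcomes.* This stands too. The benefits that Section 6 claims for the technique are a shorter learning curve, less operating time and less difficulty. Of these only operative time is an endpoint, and it stays with the unmasked surgeon, as do tracts, mucosal injury and probably re-intervention decisions.

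3. *The means are not all in place.* A reader might take the Section 22 codes as arm masking already available. They replace identities, not arms, so a separate label is needed. Section 5 also gives the postgraduate all data collection, so someone else must hold the allocation and the operative data until they are merged.

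4. *The upper figures need a strong assumption.* A rate of 20% to 30% requires four or five of ten failures to be recoded, in one arm only. That is why the milder rows are shown beside it. No similar figure is offered for pain, because the patient supplies that score.

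5. *Coded analysis is often left to the analysis plan.* This is fair as far as the A/B label goes, and its absence alone would not be a finding. It does not answer the gap in outcome recording.

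**Conclusion.** The point holds in a limited form. Section 17 masks the patient only. It plans no masked recording of postoperative outcomes and no masked analysis, although Section 5 names a person apart from the operating study leader who could do both. The protocol does not establish that bias will occur.

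Under assumed rates (50 per arm, 80% clearance, no true difference), 2.5 recoded patients in one arm would about double the false-positive rate, to 10.6%, and four or five would take it to about 20% to 30%. At 90% clearance the effect is smaller, at 70% larger. The clearance figures apply only if clearance is read after the operation.

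This is a worthwhile, low-cost improvement. Its absence does not by itself invalidate the trial.

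**What to change.** Add to Section 17:

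- The postgraduate who records postoperative outcomes (stone clearance where it is read from postoperative imaging, fever, bleeding, renal function, steinstrasse, chest complications) stays out of the operating room and does not see the allocation or the operative note until those outcomes are locked.
- The surgeon records operative time, number of tracts, mucosal injury and any re-intervention decision on a separate sheet. The protocol acknowledges these outcomes as unmasked.
- The analysis uses an A/B arm label, distinct from the Section 22 identity codes, and the label is broken only after the analysis has been run.

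Cost: one paragraph, a separate intraoperative sheet that must be kept and later merged, and someone other than the postgraduate to hold the allocation until then. No added staff, visits or procedures are needed.
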